7.1.3 Other study parameters (if applicable)

A set of patient characteristics and clinical parameters is used for baseline characteristics of the control and intervention group:

- age, gender, weight, BMI
- parameters for EORTC/MSG classification
- underlying medical condition and previous/ongoing treatment for haematological malignancies
- co-medication: agents which influences pharmacokinetics of voriconazole, immunosuppressive agents (corticosteroids, ciclosporin, MMF)
- Pharmacogenetics (CYP450 2C9 and 2C19)
- For the economical evaluation (cost effectiveness if TDM) of this study the costs of both treatment arms are evaluated. The costs of hospital and ICU stay, diagnostic procedures, used medication and blood product are evaluated, Also quality of life and production loss is evaluated after release from the hospital.
- for detailed information see CRF.

7.2 Randomisation, blinding and treatment allocation

Randomization by a computer-generated randomization system determines the sequence within in each cluster (TDM of standard of care).

7.3 Study procedures

- 1) At day two of fever the patients is informed about the study and a 24 hour period is given to think of participation.
- 2) The haematologist, in consultation with a medical microbiologist or infectious diseases specialist, will decide to start voriconazole therapy in a patient with suspected IA based on EORTC/MSG criteria. A HRCT scan is crucial part of the procedure for diagnosing the invasive fungal disease. Triggers for ordering an HRCT include detection of galactomannan in serum or plasma, pulmonary complaints or abnormalities seen on X-ray and unexplained fever of > 4 days despite broad-spectrum antibiotic therapy. A HRCT is performed at start of voriconazole treatment +/- 3 days.
- 3) Voriconazole serum concentrations after the 5th dosage (IV 6mg/kg for the first 24 hours followed by 4mg/kg bid, PO 400mg for the first 24 hours followed by 200mg bid) will be measured in all patients during treatment with voriconazole during the TDM period. Two blood samples will be drawn, one immediately before the dose (t= 0) and one 2h after the dosage (t=2) when administered orally or 1h after the end of infusion

when administered intravenously. If the serum trough level is < 2.0 mg/L the dosage will be increased. If the serum trough level is > 5mg/L the dosage will be reduced. Dosage adjustment will be performed according to a standard algorithm. Also a sample (5ml) will be drawn to assess CYP450 2C9 and 2C19 polymorphisms.

- 4) Three days after dosage adjustment a control sample series is drawn, followed by the same dose adjustment algorithm.
- 5) After reaching the therapeutic window trough levels, surveillance samples will be drawn twice a week while the patient is in the hospital. For outpatient treatment trough levels will be drawn at regular visits of the patients to the outpatient clinic (about once every two weeks). Since outpatients are clinically more stable, fluctuations are expected to be less frequent, moreover patients are often put on voriconazole during hospital stay and have a stable level when leaving the hospital. In the period without TDM, serum samples will be stored and used later to evaluate serum trough levels during the standard care episode. During this period, no additional vena punctures will have to be performed for the purpose of the study as the blood samples will be taken during regular sampling on the morning round. In total 16-54ml will be drawn depending on the duration of treatment.
- 6) After release from the hospital the patient receives at 2 weeks, 3 months, 6 months and 1 year after release a questionnaire to assess the quality of life and production loss.

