7.1.2 Secondary study parameters/endpoints (if applicable)

- 1) mortality at day 28 and week 12 of therapy due to fungal infection, overall mortality at 28 days and 12 weeks.
- 2) resolution of neutropenic fever, defined as percentage of patients with a oral temperature of $<38\text{ }^{\circ}\text{C}$ at day 7 of voriconazole treatment [17]; time (in days) to resolve fever is also noted.
- 3) percentage of voriconazole serum concentrations within the targeted window of 2-5mg/L during therapy based on repeated measurements in time.
- 4) percentage switched to salvage therapy (i.e. amphotericin B or one of its lipid or liposomal formulations; or echinocandin (e.g., caspofungin/anidulafungin) or other triazole (e.g., posaconazole); or measured concentration level in control arm during treatment for toxicity or failure)

- 5) side effects (visual disturbance and liver enzymes) Side effects leading to drug discontinuation.
- 6) time (in days) of to global response as defined under the primary endpoint definition after the start of voriconazole
- 7) The evaluation of cost-effectiveness (hospital and societal per perspective) of voriconazole TDM in patients with invasive aspergillosis will be an integral part of this project.

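### Secondary endpoint 3 sets scheduled TDM-period levels that continue after discharge against control levels with no stated sampling days, dose times or outpatient provision

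*Protocol*

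**What the plan says.** Endpoint 3 in Protocol section 7.1.2 is the "percentage of voriconazole serum concentrations within the targeted window of 2-5mg/L during therapy based on repeated measurements in time". It does not say which samples count, and it is not restricted to troughs or to time in hospital.

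Section 7.3 sets out TDM-period sampling in steps. After the fifth dose, "Two blood samples will be drawn, one immediately before the dose (t= 0) and one 2h after the dosage (t=2) when administered orally", with a corresponding post-infusion time for intravenous treatment. Then: "Three days after dosage adjustment a control sample series is drawn, followed by the same dose adjustment algorithm". Once a patient is in the window, "surveillance samples will be drawn twice a week while the patient is in the hospital". After discharge: "For outpatient treatment trough levels will be drawn at regular visits of the patients to the outpatient clinic (about once every two weeks"). Section 6.6 repeats these rules, including the outpatient one, under a sub-heading for the intervention group.

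On the control period, section 7.3 item 5 says: "In the period without TDM, serum samples will be stored and used later to evaluate serum trough levels during the standard care episode". It adds that no extra puncture is needed for the study because "the blood samples will be taken during regular sampling on the morning round". The protocol says nothing more about how stored control samples are scheduled.

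**The concern.** Endpoint 3 is the only listed endpoint that measures exposure. The rationale in section 6.6 is that TDM brings sub-therapeutic levels (25-60% of cases) and toxic levels (10-25%) each below 10%. If the primary result is null, endpoint 3 has to separate two explanations: TDM did not change exposure, or exposure changed and outcome did not. That needs the two periods to be sampled over the same part of treatment and by the same rule.

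As written they are not. TDM sampling is scheduled, is driven in part by the previous level, and continues after discharge. Control sampling has a stated purpose and one named source, a ward procedure, but no schedule. An analysis plan can choose among samples that exist. It cannot supply clinic serum that was never stored or dose times that were never recorded.

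**Working it through.** The plan gives no figure for endpoint 3 to reproduce, and the sample size in section 4.4 does not use concentrations. The main check is therefore a comparison of the sampling rules.

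| Feature | TDM period (6.6, 7.3) | Control period (7.3 item 5) |
|---|---|---|
| Initial samples | Pre-dose and timed post-dose, after the fifth dose | Not stated |
| Resampling | Series three days after each adjustment | Not stated |
| Frequency in hospital | Twice a week once in the window | Not stated; morning round |
| Time relative to dose | Stated for the initial series; surveillance levels are troughs | Meant as troughs; draw time relative to dose not stated |
| After discharge | Troughs about every two weeks | Not stated |

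Three differences follow.

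**1. Treatment time.** Outpatient levels are provided for in the TDM period only. Section 7.3 expects outpatient levels to fluctuate less, so counting them in one arm could favour that arm.

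**2. Selection by level.** A TDM patient outside the window can be resampled every three days, up to 7/3 = 2.33 series a week, against 2 surveillance samples a week for a patient inside it. If each series has two samples and both count, that is 4.67 concentrations a week against 2. A percentage over all samples then gives more weight to out-of-window TDM patients, which works against TDM.

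**3. Sample type.** The TDM series includes post-dose samples and endpoint 3 does not leave them out. Control samples are intended as troughs.

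These differences do not all act in the same direction, so the net direction is not determined.

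**Illustration of the first difference, on assumed values.** The protocol gives neither length of stay nor length of therapy. Assume therapy of 28 or 84 days (day 28 and week 12 are outcome time points, not treatment lengths) and stays of 14 to 28 days. Then:

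- inpatient surveillance samples = 2 × stay/7
- outpatient samples = (therapy − stay)/14
- outpatient share = outpatient/(inpatient + outpatient + k), where k is the number of initial and repeat-series samples

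The table uses k = 0 (surveillance only) and k = 4 (one initial and one repeat series of two samples each).

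| Stay / therapy (days) | Inpatient | Outpatient | Share, k = 0 | Share, k = 4 |
|---|---|---|---|---|
| 14 / 84 | 4 | 5 | 5/9 = 0.56 | 5/13 = 0.38 |
| 28 / 84 | 8 | 4 | 4/12 = 0.33 | 4/16 = 0.25 |
| 14 / 28 | 4 | 1 | 1/5 = 0.20 | 1/9 = 0.11 |
| 21 / 28 | 6 | 0.5 | 0.5/6.5 = 0.08 | 0.5/10.5 = 0.05 |

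Let w be the outpatient share and d the difference in in-window percentage between outpatient and inpatient levels. The TDM percentage then moves by w × d relative to inpatient levels alone. With w from 0.1 to 0.5 and d from 5 to 20 points, the shift runs from 0.1 × 5 = 0.5 points to 0.5 × 20 = 10 points; w = 0.3 and d = 10 give 3 points. The protocol supplies neither w nor d, so these figures show scale only.

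**The case against.** Several stronger readings are tempting, and the protocol does not support them.

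- *Control samples are unrelated to the dose.* Section 7.3 stores them to evaluate troughs, so pre-dose levels are intended. What is missing is a stated draw time and its record. The case report form, to which section 7.1.3 refers and which is not shown, may hold those times.
- *Morning-round control samples differ in timing from TDM samples.* The Summary places the TDM sample at routine early-morning sampling too, so a systematic time-of-day difference is not established.
- *TDM levels are all pre-dose.* They are not: the series has a post-dose sample.
- *Control levels come from inpatients only.* The text does not say so, and the outpatient sentence in section 7.3 names no arm. Item 5 also gives a total blood volume that depends on treatment duration, without naming an arm. Section 6.5 allows control levels on request for toxicity or failure.

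The first three stand as limits on the point. The fourth stands only in part. The inpatient reading is an inference, but the natural one: the outpatient sentence sits in the TDM sequence before the text turns to the control period, and section 6.6 places the same rule under the intervention group. Levels requested for toxicity or failure would be selected samples and would not restore comparability.

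It is also fair to say that restricting endpoint 3 to certain samples is an ordinary matter for an analysis plan, which may exist. That disposes of the choice of analysis set, but not of what is collected.

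**Conclusion.** The point holds in a limited form. Followed as written, section 7.3 gives endpoint 3 a scheduled, partly level-driven TDM sample set that runs past discharge. The control set has no stated days, no recorded time relative to the dose and no outpatient provision. The endpoint counts concentrations over all of therapy, so the two periods are not compared on the same treatment time or on similarly selected samples.

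Neither the size nor the net direction of the effect can be derived from the protocol. The 0.5 to 10 points cover outpatient coverage alone and rest wholly on assumed shares and differences. A reader might infer from assumed stays that control sampling misses a definite fraction of treatment; the protocol supports no such figure. The conclusion also assumes that the outpatient rule is for the TDM period only, which is the natural reading but not an explicit statement.

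The endpoint is secondary. The primary endpoint and the sample size use no concentrations and are not affected. The change is worth making because the data cannot be recovered afterwards.

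**What to change.** In section 7.3 item 5:

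- store control serum in hospital on a stated schedule that matches the TDM surveillance frequency;
- store control serum from routine outpatient draws as well;
- record the draw time and the last-dose time for every sample in both periods.

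For endpoint 3 in section 7.1.2:

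- define the main comparison on inpatient pre-dose levels, with post-dose samples left out;
- apply the same timing rule in both arms; excluding untimed samples in the control arm only would create a new asymmetry;
- use a per-patient or repeated-measures summary, so that patients sampled more often do not dominate;
- show outpatient levels separately by arm.

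The cost is protocol wording, two recorded times per sample and a few stored tubes from draws already made. Section 10.2 already asks control patients whether control samples can be drawn and does not limit the setting. The downside is that samples without a confirmed pre-dose time drop out of the main comparison in both arms.

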7.4 Withdrawal of individual subjects

Subjects can leave the study at any time for any reason if they wish to do so without any consequences. Withdrawal from the study means that the patient does not allow the investigator to use the medical data for study purposes (intervention group) or does not allow the investigator to use the medical data for study purposes and taking control samples (control period).

7.4.1 Specific criteria for withdrawal (if applicable)

7.5 Replacement of individual subjects after withdrawal

7.6 Follow-up of subjects withdrawn from treatment

7.7 Premature termination of the study

If evidence from this study or from other studies (grade A1) becomes available that therapeutic drug monitoring of voriconazole is better or worse than dosing according to dosing according to product leaflet the proceeding of the study will be discussed and the METc will be informed.

8. SAFETY REPORTING

8.1 Section 10 WMO event

In accordance to section 10, subsection 1, of the WMO, the investigator will inform the subjects and the reviewing accredited METC if anything occurs, on the basis of which it appears that the disadvantages of participation may be significantly greater than was foreseen in the research proposal. The study will be suspended pending further review by the accredited METC, except insofar as suspension would jeopardise the subjects' health. The investigator will take care that all subjects are kept informed.

8.2 Adverse and serious adverse events

Adverse events are defined as any undesirable experience occurring to a subject during a clinical trial, whether or not considered related to the investigational drug. All adverse events reported spontaneously by the subject or observed by the investigator or his staff will be recorded.

A serious adverse event is any untoward medical occurrence or effect that at any dose results in death;

- is life threatening (at the time of the event);
- requires hospitalisation or prolongation of existing inpatients' hospitalisation;
- results in persistent or significant disability or incapacity;
- is a congenital anomaly or birth defect;
- is a new event of the trial likely to affect the safety of the subjects, such as an unexpected outcome of an adverse reaction, lack of efficacy of an IMP used for the treatment of a life threatening disease, major safety finding from a newly completed animal study, etc.

All SAEs will be reported to the accredited METC that approved the protocol, according to the requirements of that METC.

8.2.1 Suspected unexpected serious adverse reactions (SUSAR)

Adverse reactions are all untoward and unintended responses to an investigational product related to any dose administered.

Unexpected adverse reactions are adverse reactions, of which the nature, or

severity, is not consistent with the applicable product information (e.g. Investigator's Brochure for an unapproved IMP or Summary of Product Characteristics (SPC) for an authorised medicinal product).

The sponsor will report expedited the following SUSARs to the METC:

- SUSARs that have arisen in the clinical trial that was assessed by the METC;
- SUSARs that have arisen in other clinical trial of the same sponsor and with the same medicinal product, and that could have consequences for the safety of the subjects involved in the clinical trial that was assessed by the METC.

The remaining SUSARs are recorded in an overview list (line-listing) that will be submitted once every half year to the METC. This line-listing provides an overview of all SUSARs from the study medicine, accompanied by a brief report highlighting the main points of concern.

The sponsor will report expedited all SUSARs to the competent authority, the Medicine Evaluation Board and the competent authorities in other Member States.

The expedited reporting will occur not later than 15 days after the sponsor has first knowledge of the adverse reactions. For fatal or life threatening cases the term will be maximal 7 days for a preliminary report with another 8 days for completion of the report.

8.2.2 Annual safety report

In addition to the expedited reporting of SUSARs, the sponsor will submit, once a year throughout the clinical trial, a safety report to the accredited METC, competent authority, Medicine Evaluation Board and competent authorities of the concerned Member States.

This safety report consists of:

- a list of all suspected (unexpected or expected) serious adverse reactions, along with an aggregated summary table of all reported serious adverse reactions, ordered by organ system, per study;
- a report concerning the safety of the subjects, consisting of a complete safety analysis and an evaluation of the balance between the efficacy and the harmfulness of the medicine under investigation.

8.3 Follow-up of adverse events

All adverse events will be followed until they have abated, or until a stable situation has been reached. Depending on the event, follow up may require additional tests or medical procedures as indicated, and/or referral to the general physician or a medical specialist.

8.4 Data Safety Monitoring Board (DSMB)

An independent expert panel (EPHO) of three specialists in the field of haemato-oncology, radiology, and mycology, and who are unaware of allocation to either of the two arms of the study (intervention or control), will classify all documented aspergillosis according to the EORTC/MSG criteria. This independent expert panel will also be involved in safety follow up (toxicity differences between the two arms) and premature termination of the study (grade A1 evidence that TDM of voriconazole improves outcome).

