3. STUDY DESIGN

As the number of patients treated for invasive aspergillosis in each hospital is limited, a multi centre set up is required to have a study powered to detect a clinically relevant difference in outcome between the intervention group and the control group. For this study a cluster randomized design - instead of a randomisation at patient level - was chosen to minimize logistic problems, optimize inclusion of patients and limit bias during the study. Blinding the intervention would increase the costs of the study considerably without providing better results. The cross-over design was chosen to diminish influences by centre, as the inter-centre variability in facility and treatment can influence outcome of treatment. Differences which are found can now be attributed solely to the intervention as the centre serves as its own control. As this study will be performed in several centres with random start with standard care or with TDM-tailored treatment, we anticipate that the time-based biases will be negligible. To diminish the carry-over effect from one period to the next a wash-out period of 28 days is established, which equals the time of start of treatment until evaluation on the primary endpoint. This prevents that two treatment protocols, intervention and control are operational at the same time. For these reasons we choose a cluster randomized cross-over design in which every cluster receives both interventions during two consecutive periods (TDM and standard care, 12 months each). This longitudinal design was previously successfully used in the Netherlands [32]. Randomization by a computer-generated randomization system determines the sequence within in each cluster. In this way the variability between clusters is taken into account, this results in an improved power. The randomization will be stratified to obtain equally balanced clusters with respect to experience and size. At six months, inclusion will be evaluated and it will be estimated whether duration per period has to be increased or decreased and whether the clusters are still balanced. The intervention (TDM) consists of taking serum samples at day three of treatment, measuring the voriconazole serum levels and adjusting the dosage to reach the therapeutic window. Dosing of voriconazole will be done during the control period according to the product brochure.

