Response to treatment will be evaluated at day 7 (fever), day 28 (primary endpoint) and at 12 weeks after start of therapy (mortality). Assessment of quality of life will be performed after release from the hospital at different time points (2 weeks, 3 months, 6 months and 1 year). Cost effectiveness from hospital perspective will be evaluated after release from the hospital. Cost effectiveness from societal perspective will be evaluated after 1 year after start of the treatment.

An expert panel (EPHO) of three specialists in the field of haemato-oncology, radiology, and mycology, and who are unaware of allocation to either of the two arms of the study (intervention or control), will classify all documented aspergillosis according to the EORTC/MSG criteria [33,45] and will report the likelihood whether fever was caused by: drug fever (e.g. cytarabine), mucositis, malignancy, Graft –Versus-Host Disease, or infection and a likelihood whether mortality was caused by fungal infection or progression of malignancy or any other cause, using protocol-defined criteria. Likelihood will be presented on a scale of 0/3 till 3/3. The evaluation of endpoints by an independent expert panel excludes investigators' bias [34, 35]. At the end of the study the EPHO, unaware of allocation to either of the two arms of the study (intervention or control), will review each patient on the primary and the following secondary endpoints 1, 2, 5 and 6. After the review of the independent expert panel the multi disciplinary study team, consisting of haematologists, infectious diseases specialists, radiologists, pharmacists, medical microbiologists, a biostatistician and a MTA expert will analyze the data on all endpoints using the outcome of the pre-screening of the expert panel.

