11. ADMINISTRATIVE ASPECTS AND PUBLICATION

11.1 Handling and storage of data and documents

Data is handled confidentially. A subject identification code list is used to link the data to the subject. The code is based on a clusternumber, abbreviation of the center and number of inclusion (e.g. 1-UMCG-12). The key to the code should be safeguarded by the investigator. The handling of personal data complies with the Dutch Personal Data Protection Act.

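### The panel that must classify the primary endpoint blind to arm is also asked to follow toxicity by arm and take part in stopping, so its blinding is not secured

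*Protocol*

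**What the plan says.** Treatment is not blinded. Section 3 of the protocol explains: "Blinding the intervention would increase the costs of the study considerably without providing better results". Protection against biased assessment is placed in a three-member expert panel (EPHO), of which section 3 says: "The evaluation of endpoints by an independent expert panel excludes investigators' bias". Its endpoint review comes last: "At the end of the study the EPHO, unaware of allocation to either of the two arms of the study" is to review every patient on the primary endpoint and on secondary endpoints 1, 2, 5 and 6. Endpoint 5 is side effects, including those that lead to discontinuation. The study team then analyses the data "using the outcome of the pre-screening of the expert panel".

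Section 8.4, headed Data Safety Monitoring Board, repeats that the panel does not know the allocation. It then adds: "This independent expert panel will also be involved in safety follow up (toxicity differences between the two arms) and premature termination of the study". The termination task is tied to high-grade evidence that TDM improves outcome. Section 7.7 lets such evidence come from this study as well as from others. No other monitoring body is named.

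On identification, section 11.1 says of the subject code: "The code is based on a clusternumber, abbreviation of the center and number of inclusion (e.g. 1-UMCG-12". Section 3 fixes the arm by centre and 12-month period. Section 7.2 randomises the order within each centre.

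**The concern.** Two adjoining sentences of section 8.4 are hard to satisfy together. A body that follows toxicity by arm, and takes part in a decision on whether TDM is better, would ordinarily learn something about the arms. Its endpoint review at the end of the study comes after that work. The protocol provides no masked labels, no separation of roles and no rule on what the panel receives.

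This matters because the blinded panel is the only stated safeguard for the primary endpoint of an open-label trial. The failure category in section 7.1.1 joins death, which is objective, to worsening disease, which has to be judged against stable disease. Toxicity is also close to the primary endpoint. The summary describes that endpoint as combining toxicity and response, and section 4.4 counts patients who stop for voriconazole adverse effects as failures. Following toxicity by arm may therefore mean following part of the primary outcome by arm.

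Allocation by centre and period adds to the exposure, because patients in the same centre and period share an arm.

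**Working it through.** **1. The passages side by side**

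| Place | Panel's task | Arm knowledge |
|---|---|---|
| Section 3 | Classify the primary endpoint and secondary endpoints 1, 2, 5, 6 at the end of the study | Stated blind |
| Section 8.4, first sentence | Classify aspergillosis | Stated blind |
| Section 8.4, second sentence | Toxicity by arm; premature termination | Not stated; the task concerns arm differences |
| Section 7.7 | Stopping evidence may come from this study | Not stated |

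The protocol does not say whether toxicity is shown under masked labels, whether the panel sees the subject code or dates, or whether it knows any centre's sequence.

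**2. The plan's own sample size (section 4.4)**

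Inputs: failure 40% against 20%, two-sided 5%, power about 80%, 12 centres of 16 patients, correlation up to 0.02. Without clustering, the two-proportion formula gives 82 per arm, or 164 in total. With m = 8 per centre-period, and reading the most unfavourable case as no correlation across periods (an assumption):

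- design effect = 1 + (8 − 1) × 0.02 = 1.14
- 82 × 1.14 = 93.5, rounded up to 94 per arm, or 188 in total

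This is close to the stated 192, at which power is 0.814. The point does not depend on this figure; it only fixes N and the design effect used in step 5.

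**3. Patients who share an arm**

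192 / 12 / 2 = 8 per centre-period. With the 13 centres of section 4.1 and 200 patients, it is 200 / 13 / 2 = 7.7. If centre and period are visible, one known arm gives the arm of about 8 patients. Because each centre crosses over, it also gives the other period, so 2 × 8 = 16.

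**4. What the subject code reveals**

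The code shows centre and order of inclusion. Without the centre's sequence it separates early from late patients but does not say which arm came first. Suppose the sequence is known and the 16 inclusion numbers are cut at 8. If each patient falls in either period with probability 1/2 (an assumption), the number misassigned is |K − 8|, with K binomial(16, 1/2):

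- E|K − 8| = 8 × 12870 / 65536 = 1.57
- share assigned correctly = (16 − 1.57) / 16 = 0.90

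**5. What biased classification would do (illustration)**

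Assume no true effect, 40% failure in both arms, and knowledge of arm lowering the classified TDM failure rate by s. With n = 96 / DE per arm, p1 = 0.40, p2 = 0.40 − s and p̄ their mean:

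- se0 = √(2p̄(1 − p̄)/n)
- se1 = √((p1(1 − p1) + p2(1 − p2))/n)
- rejection rate = Φ((s − 1.96·se0)/se1) + Φ((−s − 1.96·se0)/se1)

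For s = 0.05 and DE = 1: se0 = 0.0699 and se1 = 0.0698. The rate is Φ(−1.246) + Φ(−2.679) = 0.106 + 0.004 = 0.110.

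| s | DE = 1.00 | DE = 1.14 |
|---|---|---|
| 2 points | 5.9% | 5.8% |
| 5 points | 11.0% | 10.2% |
| 10 points | 30.5% | 27.4% |

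Nothing in the protocol says which row, if any, would apply.

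**The case against.** The protocol states twice that the panel does not know the allocation. Toxicity can be compared in aggregate under masked labels, and even an unmasked aggregate table does not show which patient was in which arm. High-grade evidence on TDM could also come from outside the trial, and weighing it would need no arm data. What is left out of dossiers is often settled in a panel charter, which is not at hand. All this stands, and it limits the point to blinding that is not secured. It does not remove the point: masked labels are not provided for, section 7.7 admits evidence from this study, and judging whether TDM is better requires knowing which arm is TDM.

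A reader might go further, and the documents do not support the following readings:

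- **The subject code gives away the arm.** The sequence is randomised per centre, period length may be changed after the six-month evaluation, and nothing says the panel receives the code.
- **One drug level in a dossier unmasks a centre-period.** Section 6.5 allows levels to be requested for toxicity or failure, and secondary endpoint 4 expects measured levels in the control arm. A level alone does not identify TDM.
- **Judging cause of death biases the primary endpoint.** Section 7.1.1 counts death as failure whatever its cause. Cause matters for secondary endpoint 1.
- **Calling the review a pre-screening lets the study team overrule it.** The text gives the team no such power. It also does not say that the panel's classification is final.

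**Conclusion.** Section 8.4 is internally inconsistent about the panel, and it conflicts with the blinded review on which section 3 relies. Followed as written, the plan puts the blinding of the primary endpoint at risk. A reader might infer that the blinding has already failed, but the text does not show that: it never says the panel sees patient-level allocation, unmasked arms or the subject code.

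Any bias in the primary endpoint would act mainly through the choice between worsening and stable. Its size is unknown. The error rates of about 6%, 10-11% and 27-31% rest entirely on assumed shifts of 2, 5 and 10 points with no true effect. The group of about 8 patients follows from the plan's own numbers, but it matters only if centre and period are visible to the panel. Should-fix, with moderate confidence.

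**What to change.** 1. **Dossiers.** Send them to the panel under random review numbers, shuffled over centres and periods. Remove centre, inclusion number, calendar dates, drug levels and dose adjustments. Keep days since the start of treatment and any discontinuation for adverse effects, which the panel must assess.
2. **Roles.** Reconcile sections 3 and 8.4 so that the panel receives no unmasked by-arm data and no patient-level allocation until its classifications are locked. Any toxicity comparison it sees during the trial is aggregate and under masked labels. Add an unmasked by-arm table explicitly to the safety report to the METC, since section 8.2.2 now asks only for a table for the study as a whole. Termination questions that need the arms identified go through section 7.7, which should then say who weighs that evidence, because it now names no deciding body.
3. **Analysis.** State that the locked panel classification is the one analysed.

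The cost is data-management time for renumbering and redaction, plus amendment wording. The downside is that during the trial the panel, the only body named under the DSMB heading, sees safety by arm only under masked labels. That is why the by-arm table for the METC has to be written in and cannot be assumed.
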